Low-load blood flow restriction (LL-BFR) training has emerged as an innovative rehabilitation strategy that combines low-intensity resistance exercise with partial vascular occlusion to enhance muscle growth and strength while using much lower loads than traditional resistance training (Hughes et al., 2017). Evidence suggests that BFR can safely stimulate muscle hypertrophy comparable to high-load training and may reduce joint stress, making it particularly suitable for patients recovering from ACLR (Scott et al., 2015). This pilot study aims to compare the effectiveness of LL-BFR and traditional resistance training in improving muscle size, strength, range of motion, pain, and joint effusion in patients following ACLR, contributing to the evidence base for optimal post-surgical rehabilitation strategies.

Objective

The main objective/s of the study is to compare the effectiveness of low load blood flow restriction training (LL-BFR) with traditional resistance training exercises (T-RT) at improving skeletal muscle hypertrophy, strength, Range of motion (ROM), pain and effusion in individuals who have undergone anterior cruciate ligament (ACL) reconstruction surgery.

Study Design

1. Study Type

Interventional: The study (Pilot randomized controlled trial) involves an active intervention (BFR-RT vs. T-RT) to evaluate treatment efficacy.

2. Primary Purpose

Treatment: The study aims to assess the therapeutic effectiveness of BFR-RT compared to traditional low load training in improving post-ACLR outcomes.

3. Study Phase

N/A: The trial does not involve investigational drugs or biologics.

4. Intervention Model

Parallel Design: Two distinct groups receive different interventions simultaneously:

Group 1 (BFR-RT): Low-load resistance training with blood flow restriction along with standard rehabilitation.

Group 2 (T-RT): Low-load traditional resistance training with standard rehabilitation.

- **Model Description:**

BFR-RT group undergoes 8 weeks of BFR training followed by standard rehabilitation protocol progression.

T-RT group receives standard rehabilitation alone for the entire duration.

5. Number of Arms

2 Arms:

Experimental Arm: BFR-RT.

Active Comparator Arm: T-RT.

6. Masking (Blinding)

- **Single-Assessor Blinded:**

Investigator: The researcher assessing outcomes is blinded to group assignments.

Participant: Participants are aware of their group (open-label for participants).

Care Provider: Therapists administering interventions are unblinded.

None (Open Label): Not applicable; partial blinding is used.

6. Allocation

Participants are randomly assigned to BFR-RT or T-RT groups.

Method: Opaque envelopes with coded assignments prepared by an independent team member.

Stratification: Not specified, but typically balanced for age, sex, or baseline function.

7. Enrollment

- Target Sample Size: 32 participants.

Type: Actual (confirmed enrolled participants).

Justification: Based on power analysis to detect clinically significant differences in muscle hypertrophy/strength.

8. Additional Protocol Details

Intervention Protocol

Frequency: Biweekly sessions (16 total over 8 weeks).

BFR Technique:

- Occlusion band placed proximally on the affected limb.
- Tightness standardized to allow one finger beneath the band.

Standard Rehabilitation:

- Includes range of motion (ROM) exercises, strengthening, and functional training per hospital protocol.

Outcome Assessments

Time Points: Baseline (Week 0-1), Mid-Intervention (Week 4-5), Post-Intervention (Week 9).

Measures:

Primary: Muscle hypertrophy (ultrasound/MRI), strength (manual muscle testing).

Secondary: Pain (KOOS), knee ROM, effusion (circumference), adherence rates.

Safety Monitoring

- Adverse Events: Documented throughout; none reported in this trial.
- Exclusion Safeguards: No vascular pathologies or anticoagulant use.

9. Ethical Considerations

Informed Consent: Obtained from all participants.

Approval: Ethical approval was taken from the Institutional Review Board (IRB) of Rehman Medical Institute.

10. Participants:

- **Inclusion criteria:** Individuals who have undergone ACL reconstruction surgery within the past 4 weeks, free of any neurological impairments or significant cardiac, pulmonary, or metabolic conditions.
- **Exclusion criteria:** Individuals with contraindications to exercise, any other comorbidity, or systemic inflammatory conditions.

Outcome Measures:

- **Primary Outcome:** Muscle strength (measured using manual muscle technique). Muscle size (measured via measuring tape), ROM (Using goniometer), pain (using a Visual Analog Scale), and joint effusion (assessed clinically).

Statistical Analysis Plan

This Statistical analysis plan (SAP) compares postoperative rehabilitation outcomes between an experimental training group (n=16) and a control group (n=16) across three key timepoints: immediate post-surgical baseline (0-1 week), mid-intervention (4-5 weeks), and post-intervention (8-9 weeks). The study employs a repeated measures design to evaluate five primary outcome domains: muscle size (continuous, cm), range of motion (continuous, degrees), muscle strength (ordinal, 0-5 scale), pain perception (ordinal, VAS 0-10), and joint effusion (ordinal, 0-3 clinical scale).

In contrast, This SAP includes descriptive statistics, normality assessments, inferential statistical tests with corresponding assumptions, multiple comparison adjustments, missing data handling procedures, and software implementation to ensure reproducibility.

1. Descriptive Statistical Approaches

Comprehensive descriptive analyses will precede all inferential testing to characterize the dataset and inform appropriate test selection. For continuous variables (muscle size, ROM), we will report means with standard deviations (SD) for normally distributed data and medians with interquartile ranges (IQR) and full ranges for non-normal distributions, supplemented by graphical representations including boxplots with superimposed individual data points to visualize both group trends and individual trajectories. Ordinal variables (strength, pain, effusion) will be summarized using median scores with IQRs and frequency distribution tables showing counts/proportions at each ordinal level, with stacked bar charts employed to visualize proportional changes across timepoints. These descriptive analyses will be stratified by group (experimental vs control) and timepoint to enable preliminary assessment of intervention effects and data distributions prior to formal hypothesis testing.

2. Data Characteristics and Variable Classification

The dataset comprises both continuous and ordinal variables requiring distinct analytical approaches. Continuous variables including muscle circumference (measured via standardized tape measure protocol) and active range of motion (measured via goniometry by blinded assessors) will be analyzed for both central tendency and variability. Ordinal variables including manual muscle testing scores (Medical Research Council 0-5 scale), visual analog pain scores (recorded as integers 0-10), and clinician-rated effusion scales (0=none, 3=severe) will be analyzed using non-parametric methods due to their inherent rank-based properties and expected non-normal distributions. All variables will be assessed at three protocol-specified timepoints with identical measurement protocols maintained across groups to ensure comparability.

3. Normality and Parametric Assumption Testing

Formal statistical testing for normality assumptions will be conducted for all continuous variables prior to selecting inferential methods. The Shapiro-Wilk test ($\alpha=0.05$) will be applied to residuals from all continuous outcome measures within each group-by-time combination, supplemented by visual inspection of Q-Q plots and histograms to detect deviations from normality that may not reach statistical significance in small samples. Homogeneity of variance between groups will be verified using Levene's test for equality of variances when parametric between-group comparisons are planned. For instances where normality or homogeneity assumptions are violated (Shapiro-Wilk $p\leq0.05$ or Levene's $p\leq0.05$), pre-specified non-parametric alternatives will be implemented as detailed in subsequent sections. All assumption testing results will be documented in supplementary materials to demonstrate the appropriateness of selected analytical methods.

4. Primary Inferential Statistical Methods

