4.1 Within-Group Longitudinal Analyses

For evaluating changes over time within each experimental arm, distinct approaches will

be employed based on variable characteristics. Continuous variables meeting normality assumptions will be analyzed using repeated measures ANOVA with Greenhouse-Geisser correction for sphericity violations, followed by paired t-tests with Bonferroni-adjusted α levels for post-hoc timepoint comparisons when omnibus tests reach significance. Non-normal continuous data and all ordinal outcomes will utilize the Friedman test (non-parametric equivalent to repeated measures ANOVA) followed by Wilcoxon signed-rank tests for post-hoc comparisons with appropriate multiplicity adjustments. Effect sizes will be reported as Cohen's d for parametric analyses and rank-biserial correlations for non-parametric tests to quantify the magnitude of observed changes independent of sample size considerations.

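### Protocol Section 8 names two primary outcomes, the Outcome Measures heading and the SAP name five with partly different instruments, and SAP 4.2 has no multiplicity rule or decisive visit for the between-arm tests

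*Combined protocol and SAP*

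**What the plan says.** **Protocol Section 8, Measures.** The primary line is "Primary: Muscle hypertrophy (ultrasound/MRI), strength (manual muscle testing"). The next line is "Secondary: Pain (KOOS), knee ROM, effusion (circumference), adherence rates".

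**Protocol, Outcome Measures.** This heading puts muscle strength by manual technique under Primary Outcome and continues: "Muscle size (measured via measuring tape), ROM (Using goniometer), pain (using a Visual Analog Scale), and joint effusion (assessed clinically"). It has no secondary list.

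**SAP introduction.** The study is to "evaluate five primary outcome domains: muscle size (continuous, cm"), followed by ROM, strength, pain and effusion. SAP Section 2 gives the instruments: "muscle circumference (measured via standardized tape measure protocol") for size, and "visual analog pain scores (recorded as integers 0-10), and clinician-rated effusion scales (0=none, 3=severe") for pain and effusion.

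**Background and Objective.** The aim at the end of the background lists muscle size, strength, ROM, pain and effusion. The Objective lists the same domains but says hypertrophy instead of size. Neither ranks them.

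**Protocol Section 7.** The 32 participants are justified by a power analysis on hypertrophy and strength, which is Section 8's pair.

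**Multiplicity.** The SAP introduction says the plan includes "multiple comparison adjustments, missing data handling procedures". Specific provisions appear only in SAP 4.1, for within-group comparisons between timepoints: Bonferroni after repeated measures ANOVA, and, after the Friedman test, "Wilcoxon signed-rank tests for post-hoc comparisons with appropriate multiplicity adjustments". SAP 4.2 covers experimental against control at each timepoint. It states no adjustment, ordering, significance level or decisive visit.

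**The concern.** The two lists differ in how many outcomes are primary, which ones they are, and how three of them are measured. A reader of the final report could not tell from these documents which result was meant to decide the trial.

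Two things are at stake. First, a between-arm difference on any one of five outcomes, at either follow-up visit, could be presented as the primary result. Strength, which is on both lists, could be presented as one of two primaries or as one of five. Second, a tape measurement could be reported as answering the hypertrophy objective, although Section 8 assigns imaging to hypertrophy and the SAP plans no analysis of imaging.

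**Working it through.** **Step 1. The lists side by side.**

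| Outcome | Section 8 | Outcome Measures and SAP | Status conflicts | Instrument conflicts |
|---|---|---|---|---|
| Muscle size / hypertrophy | Primary, ultrasound/MRI | Primary, tape | No | Yes |
| Strength | Primary, manual testing | Primary, manual testing | No | No |
| ROM | Secondary, no instrument named | Primary, goniometer | Yes | No |
| Pain | Secondary, KOOS | Primary, VAS | Yes | Yes |
| Effusion | Secondary, circumference | Primary, clinical grade (0-3 in the SAP) | Yes | Yes |
| Adherence | Secondary | Not listed | – | – |

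Primaries: 2 against 5. Status conflicts for 3 of the 5 shared domains, and the instrument for 3 of the 5. Only strength agrees on both. The SAP contains no analysis of imaging, KOOS, effusion circumference or adherence.

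**Step 2. Which list governs?** The aim, the Objective, the Outcome Measures heading and the SAP all name the same five domains, so Section 8 is the outlier. The sample-size sentence points the other way, to hypertrophy and strength. No text settles it.

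**Step 3. The plan's own figure.** The total of 32 (16 per arm) cannot be reproduced: no effect size, SD, significance level, power or dropout is given. Back-solving under an assumed two-sided 0.05 and 80% power, n per arm = 2 × (1.960 + 0.842)² / d². At d = 1.0 this is 15.7, so 16. The figure therefore fits a standardized difference of about 1.0 on one unadjusted test. That shows compatibility only; it does not reproduce the plan's calculation.

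**Step 4. False-positive chance without adjustment.** The documents state 0.05 only for the assumption checks, so two-sided 0.05 for the outcome tests is an assumption. For k independent tests the chance of at least one false positive is 1 − 0.95^k.

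- Five primaries, one visit: 1 − 0.95^5 = 22.6%.
- Section 8's two primaries, one visit: 1 − 0.95² = 9.75%.
- Five primaries, both follow-up visits: 1 − 0.95^10 = 40.1%. This is an upper illustration, because repeated measures are correlated.

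With equally correlated normal test statistics (simulation, 1,000,000 draws, |z| > 1.96), five tests at one visit give about 21%, 18% and 15% at assumed correlations of 0.3, 0.5 and 0.7.

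**Step 5. Cost of adjustment.** Holm's first step tests the smallest p-value at 0.05 / 5 = 0.01, the Bonferroni level, so Bonferroni bounds the loss. For a t-test at 16 against 16 there are 30 degrees of freedom and the noncentrality is d × √(16/2) = 2.828d.

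- At 0.05, 80% power needs d = 1.02.
- At 0.01, 80% power needs d = 1.28.
- At 0.01 with d = 1.02, power is 56%.

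These figures apply to the two continuous outcomes if they are analysed by t-test. The three ordinal outcomes use Mann-Whitney tests, and their cost depends on ties that the documents do not allow one to predict.

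**The case against.** The strongest reply has three parts.

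*Section 8 is an isolated slip.* Every other listing of the domains has five, and the SAP, which controls the analysis, is consistent with the Outcome Measures heading. The aim says muscle size, which is what the SAP measures. This stands as far as it goes, and it is why the five-outcome list is the sensible default. It does not remove the conflict, because the sample-size sentence matches Section 8 and nothing withdraws Section 8.

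*Multiplicity is covered.* The SAP announces adjustments, so it would be wrong to say that it has none. But the announcement names no method or family, and the only provisions that follow are for within-group comparisons. The gap in 4.2 remains.

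*It is a pilot.* Strict error control is not obligatory in a pilot, and 4.2 already plans mean differences with 95% confidence intervals. This largely stands: reporting all five as estimates is a legitimate repair, and Holm is not the only one. The label alone does not settle the matter, because the protocol also states an efficacy purpose and cites a power analysis.

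A reader might also infer three stronger points that the documents do not support:

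- **Outcomes were switched after results were known.** Enrolment is given as actual and no adverse events are reported, so follow-up may be advanced. Nothing shows when either list was fixed.
- **The post-intervention visit has two conflicting windows.** Week 9 in Section 8 lies within the SAP's 8-9 weeks.
- **The same circumference serves as swelling in one list and as muscle in the other.** A tape can be used at different sites for the two purposes. The site is not stated, which is missing detail and not a contradiction.

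**Conclusion.** The plan is wrong as written and must be fixed before results are interpreted. The contradiction in primary outcomes and instruments rests on the text alone and needs no assumption.

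The multiplicity gap is real but secondary to it. Its size, 22.6% if independent and about 15% to 21% under correlation at one visit, rests on an assumed two-sided 0.05 and assumed equal correlations of 0.3 to 0.7. It treats each test as holding its nominal level, and so ignores the SAP's switching between tests after the Shapiro-Wilk and Levene checks. It matters if an efficacy claim is to be made. If the trial reports estimates only, the rate shows why no single significant result should be singled out.

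**What to change.** 1. **One list, one instrument per outcome.** Reconcile Section 8, the Outcome Measures heading and the SAP. The default is the five-outcome list, because it is the only one with a full analysis plan. Keep the replaced wording in a dated change record that states when the list was fixed relative to data review. If a dated version shows that Section 8 governed, add an analysis of the imaging outcome, or state that imaging was not done; do not substitute tape for it.

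2. **SAP 4.2.** Name the post-intervention visit as decisive and the mid-intervention visit as secondary. Then adopt one of two rules:
   - If an efficacy claim is to be made: *The five between-group tests of the primary outcomes at the post-intervention visit will be adjusted by Holm's method at a two-sided family-wise level of 0.05.*
   - If it is to be read as a pilot: *All five primary outcomes will be reported as between-group estimates with 95% confidence intervals, and no confirmatory claim will be made.*

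   If the list or the visit was fixed after data were seen, label the results exploratory.

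3. **Match the claim to the measurement.** Report tape results as limb circumference, not hypertrophy, and align the Objective and the sample-size sentence.

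**Cost.** Under the default this is protocol and SAP wording with no new data. The claim becomes narrower. The estimation option gives up any confirmatory statement. Holm loses some power, bounded for the t-tests by the Bonferroni figures above (1.02 to 1.28 SD detectable; 80% to 56% power at 1.02 SD). Holm is never less powerful than Bonferroni.

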4.2 Between-Group Comparative Analyses

Experimental versus control group comparisons at each timepoint will employ independent samples t-tests for normally distributed continuous variables with equal variances, Welch's t-tests for unequal variances (as determined by Levene's test), and Mann-Whitney U tests for non-normal continuous or ordinal data. Between-group effect sizes will be reported as mean differences with 95% confidence intervals for parametric tests and Hodges-Lehmann median differences for non-parametric analyses. To account for baseline imbalances in this pilot study, exploratory analyses of covariance (ANCOVA) may be conducted for continuous outcomes using baseline measurements as covariates if substantial pre-intervention group differences are detected despite randomization.

5. Missing Data Handling Protocol

Missing data patterns will be formally evaluated using Little's MCAR test prior to primary analyses. Given the pilot nature of this study with limited sample size, primary analyses will employ complete case approaches with explicit reporting of missing data proportions by group and timepoint. Sensitivity analyses will compare complete case results with multiple imputation approaches using chained equations (MICE)

incorporating baseline characteristics and observed follow-up data as predictors. Participants with missing baseline data will be excluded from all analyses, while those missing later timepoints will be retained for analyses where their available data permits. A participant flow diagram will document attrition at each study phase.

6. Software Implementation and Reproducibility

All analyses will be conducted using Stata MP 18.0. Graphical outputs will adhere to STROND guidelines for transparent reporting of non-normal data distributions.

Reference:

Ardern, C. L., Webster, K. E., Taylor, N. F., & Feller, J. A. (2011). Return to sport following anterior cruciate ligament reconstruction surgery: A systematic review and meta-analysis of the state of play. *British Journal of Sports Medicine*, 45(7), 596–606. <https://doi.org/10.1136/bjsm.2010.076364>

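### The four-week entry window conflicts with a baseline in the first week after surgery, and if late entry is real, time since surgery is an unused covariate that costs precision but causes no bias.

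*Combined protocol and SAP*

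**What the plan says.** **Entry.** Protocol section 10 (Participants) includes "Individuals who have undergone ACL reconstruction surgery within the past 4 weeks, free of any neurological impairments", so a patient may enter from day 0 to day 28.

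**Visits.** Protocol section 8 (Outcome Assessments) lists "Baseline (Week 0-1), Mid-Intervention (Week 4-5), Post-Intervention (Week 9"), with no statement of what the weeks are counted from. The SAP introduction gives "immediate post-surgical baseline (0-1 week), mid-intervention (4-5 weeks), and post-intervention (8-9 weeks"), which suggests counting from surgery, at least for baseline.

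**Allocation.** The protocol's Allocation section says "Participants are randomly assigned to BFR-RT or T-RT groups", by opaque envelopes. On strata it says only "Stratification: Not specified, but typically balanced for age, sex, or baseline function". Time since surgery is not on that list.

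**Analysis.** SAP 4.2 compares the arms at each timepoint by t-test, Welch test or Mann-Whitney test, all unadjusted. The one adjusted analysis is optional: "exploratory analyses of covariance (ANCOVA) may be conducted for continuous outcomes using baseline measurements as covariates". It depends on a substantial baseline difference being found, without saying how large that is, and has no counterpart for strength, pain or effusion.

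**Size.** "Target Sample Size: 32 participants", 16 per arm. Enrolment is recorded as actual, not anticipated.

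**The concern.** Pain, effusion, range of motion, thigh girth and strength can all be expected to change quickly in the first weeks after reconstruction. If entry really spans four weeks, days since surgery probably predicts every outcome, and the plan neither balances it nor adjusts for it. With 16 per arm, a chance difference in recovery stage could make the observed arm difference larger or smaller, and the spread in recovery stage adds noise that a covariate could remove.

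Whether this matters depends on a prior question that the documents leave open: does week 0 mean surgery or study entry? A baseline in the first week after surgery and an entry window of four weeks cannot both describe every patient.

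**Working it through.** **1. The plan's own figure.** The sample size of 32 is attributed to a power analysis, but no effect size, SD, power or alpha is given, so it cannot be reproduced. With an assumed two-sided 5% level and 80% power, 16 per arm corresponds to a standardised difference of (1.96 + 0.84) × √(2/16) = 0.99. The plan gives no figure for time since surgery.

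**2. The two readings of the time origin.**
- *Weeks counted from surgery.* A patient who enters at week 4 has no week 0-1 baseline. The training lasts 8 weeks, so it would end at about 4 + 8 = 12 weeks after surgery, beyond the Week 9 assessment. This reading is workable only if the entry window was in practice much shorter than four weeks.
- *Weeks counted from entry.* The schedule works for everyone, but the SAP's description of baseline as immediately post-surgical does not fit a patient entering at week 3 or 4. Time since surgery then runs from 0 to 4 weeks at entry and from about 9 to 13 weeks at the Week 9 visit.

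The documents do not say which applies.

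**3. Chance imbalance between arms.** The entry distribution is not given, so entry is assumed uniform over the window. SD = window/√12, and the standard error of the difference in arm means = SD × √(2/16).

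| Entry window | SD (days) | SE of difference (days) | 95% range (days) |
|---|---|---|---|
| 0-28 days | 28/√12 = 8.08 | 8.08 × 0.354 = 2.86 | 1.96 × 2.86 = ±5.6 |
| 0-7 days | 7/√12 = 2.02 | 2.02 × 0.354 = 0.71 | 1.96 × 0.71 = ±1.4 |

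For the 28-day window, the chance of a difference above 4 days in either direction is 2 × [1 − Φ(4/2.86)] = 0.16. The expected difference is zero in both rows.

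**4. Bias and type I error.** Trials with 16 per arm were simulated (40,000 per setting), with time since surgery explaining 0, 10, 25 or 50% of outcome variance (assumed). The unadjusted estimate averaged 1.00 for a true difference of 1.0 SD, and type I error was about 5% in every setting, with or without adjustment.

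**5. Precision.** Let r be the correlation of time since surgery with outcome (assumed). Adjustment multiplies the residual SD by √(1 − r²). Estimating one more coefficient from 32 patients costs a factor of about √(1 + 1/28) = 1.018 in the standard error, and the t quantile rises from 2.042 (30 df) to 2.045 (29 df), a factor of 1.001. The combined penalty is about 1.019.

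| r | √(1 − r²) | × 1.019 | Net change in interval width |
|---|---|---|---|
| 0 | 1.000 | 1.019 | about 2% wider |
| 0.3 | 0.954 | 0.972 | about 3% narrower |
| 0.5 | 0.866 | 0.883 | about 12% narrower |

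Direct simulation of the interval widths agrees. In power terms, at an assumed true difference of 1.0 SD, the unadjusted test has about 78%. Adjustment gives about 81% at r² = 0.10 and 87% at r² = 0.25, and about 76% if time since surgery is unrelated to outcome.

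These gains are for time since surgery alone. Baseline value and recovery stage are likely to overlap, so the extra gain is smaller once the baseline value is in the model. The documents give nothing from which to estimate by how much.

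**The case against.** A reader might infer that arm differences at each visit systematically mix treatment with recovery stage. The documents do not support that. Allocation is random, so time since surgery is balanced in expectation, and the unadjusted interval and p-value already allow for chance imbalance. This part of the objection stands in full.

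A reader might also take it as settled that visits are timed from entry. No section says so, and the SAP introduction's wording points towards surgery. On that reading the spread of entry is about a week and the concern almost vanishes. This stands as far as it goes, but the 8-week training and the Week 9 assessment do not fit a four-week window counted from surgery. The conflict is therefore itself part of the point.

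The remaining objections concern the remedy. Choosing one more covariate in a 32-patient pilot is partly a matter of judgement, and the correlations are assumed. The optional baseline ANCOVA, if run, would capture recovery stage in part. Replacing rank tests with proportional-odds models for three ordinal outcomes would risk sparse categories on 0-3 and 0-5 scales. Because enrolment is already complete, a covariate added now may not be truly prespecified. All of these are fair and they limit the fix, but they do not remove the case for an inexpensive covariate in the two continuous outcomes.

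The sentence on stratification might be read as a claim that balance was secured by design. It opens by saying that strata are not specified, so it is unclear wording and carries little weight here.

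**Conclusion.** The concern holds in a limited form. The entry window and the SAP's description of baseline are inconsistent, no time origin is defined, and the passages must be reconciled. That much follows from the text alone.

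The rest is conditional. If entry up to four weeks is real, a likely prognostic factor is left out of both the allocation and the between-arm analysis. The consequence is possible chance imbalance of about ±5.6 days between arm means (uniform entry assumed) and forgone precision of about 3% to 12% of interval width (correlation 0.3 to 0.5 assumed, and less alongside the baseline value). It is not a source of systematic bias or of an inflated type I error. If all patients entered within a week of surgery, the imbalance range is about ±1.4 days and the matter is negligible.

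**What to change.** 1. **Time origin.** State whether weeks are counted from surgery or from entry, and reconcile protocol sections 8 and 10 with the SAP introduction.
2. **Reporting.** Show days from surgery to baseline by arm in the baseline table. This also shows which reading applied in practice.
3. **SAP 4.2, circumference and range of motion.** Make the between-arm analysis at the mid- and post-intervention visits an ANCOVA with the baseline outcome value and days from surgery to baseline as covariates. Run it regardless of observed imbalance, and label it post hoc if outcomes by arm have already been seen.
4. **SAP 4.2, strength, pain and effusion.** Keep the Mann-Whitney tests. Use any adjusted ordinal model as a sensitivity analysis only.
5. **Allocation section.** If no strata were used, describe the allocation as unstratified and remove the remark about typical balance. Enrolment is recorded as actual, so stratification can no longer be added.

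The cost is SAP wording and one degree of freedom for days since surgery, with intervals about 2% wider if that covariate turns out to be unrelated to outcome. No new visits or patients are needed. The surgery date should already be on file, since the entry criterion depends on it, but the sponsor should confirm that an exact date was recorded for each patient.

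### The SAP's only muscle-size measure is tape girth from an immediate post-surgical baseline, while section 8 lists imaging for hypertrophy and circumference for effusion; girth alone should not carry a hypertrophy conclusion

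*Combined protocol and SAP*

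**What the plan says.** The Objective compares the two programmes "at improving skeletal muscle hypertrophy, strength, Range of motion (ROM), pain and effusion", so muscle growth and effusion are separate targets. The documents then give two sets of instruments.

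- **Protocol section 8, Outcome Assessments.** "Primary: Muscle hypertrophy (ultrasound/MRI), strength (manual muscle testing"; and "Secondary: Pain (KOOS), knee ROM, effusion (circumference), adherence rates". Muscle is imaged and effusion is read from circumference.
- **Protocol, Outcome Measures (after section 10).** "Muscle size (measured via measuring tape), ROM (Using goniometer", and "joint effusion (assessed clinically". Muscle is taped and effusion is judged by a clinician.
- **SAP introduction and SAP section 2.** The SAP follows the second set. It has "muscle circumference (measured via standardized tape measure protocol", in cm, as a continuous variable, and effusion as a clinician-rated ordinal grade from 0 to 3. Ultrasound and MRI are not mentioned.

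The SAP introduction puts baseline at 0-1 week and describes it as immediately after surgery. Eligibility allows surgery up to 4 weeks earlier. The SAP refers to a standardised tape procedure, but neither document names a site or landmark. SAP 4.1 tests change over time within each arm. SAP 4.2 compares arms at each timepoint, with optional exploratory ANCOVA on the baseline value. No analysis relates girth to effusion.

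**The concern.** Girth is the circumference of everything under the tape. Soon after knee surgery that includes swelling, and section 8 itself treats circumference as an indicator of swelling. A larger reading can mean more muscle or more fluid; a smaller one can mean less fluid or more wasting. Under section 8 a fall in circumference is an improvement, while under the Outcome Measures list and the SAP a rise is.

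If the SAP is followed as written, the result offered for the first-named objective will be a change or difference in girth. A reader would take it as evidence about hypertrophy, although the plan neither analyses the imaging that section 8 lists nor says where the tape was placed.

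**Working it through.** **1. The plan's own figure.** The only relevant figure is the sample size of 32 (16 per arm), said to rest on a power analysis for hypertrophy or strength. No effect size, SD, significance level, sidedness, power or dropout is given for it, so it cannot be reproduced. For orientation, 80% power at two-sided 5% implies d = (1.960 + 0.842) × √(2/16) = 0.99 by the normal approximation, or 1.02 by the exact t-test. Without a stated SD this cannot be turned into centimetres of girth.

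**2. The lists side by side.**

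| Source | Muscle | Effusion |
|---|---|---|
| Protocol section 8 | ultrasound/MRI | circumference |
| Outcome Measures list | tape | clinical assessment |
| SAP | tape, cm | clinical grade 0-3 |

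Circumference serves both outcomes only when the effusion entry of the first row is joined to the muscle entry of the second or third.

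**3. How far muscle growth moves the tape.** Assumptions, none from the documents: near-circular limb, girth C = 40-50 cm, muscle fraction of the cross-section f = 0.5-0.7, gain in muscle area g. Girth change = C × (√(1 + f·g) − 1).

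- g = 5%: 40 × (√1.025 − 1) = 0.50 cm; 50 × (√1.035 − 1) = 0.87 cm.
- g = 10%: 40 × (√1.05 − 1) = 0.99 cm; 50 × (√1.07 − 1) = 1.72 cm.

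**4. Within-arm change (SAP 4.1).** Observed change = muscle change − swelling resolved. With a 5% gain and 0 to 1 cm of swelling resolved at the tape site (assumed), the net change runs from +0.87 cm (0.87 − 0) to −0.50 cm (0.50 − 1.00). There is no comparison arm in these tests to cancel the swelling.

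**5. Between-arm difference (SAP 4.2).** Observed difference = muscle difference + swelling difference. Take an arm difference of 5% in muscle area (0.50-0.87 cm) and vary the assumed arm difference in swelling:

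| Swelling difference | Share of the muscle effect |
|---|---|
| 0 cm | none |
| 0.25 cm | 29% (0.25/0.87) to 50% (0.25/0.50) |
| 0.5 cm | 57% (0.5/0.87) to 100% (0.5/0.50) |
| 1 cm | 115% (1/0.87) to 200% (1/0.50) |

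The sign depends on which arm has more swelling, so a real gain can be hidden or an absent one imitated.

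**6. The same point in SD units.** Two-sample t-test, 16 per arm, two-sided 5%, assumed true muscle difference of 1.0 SD:

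- No swelling contribution: power 78%.
- Equal mean swelling change in both arms, with swelling SD 0.5 to 1.0 times the muscle SD: the difference stays unbiased and power falls to 69% and 49%.
- Swelling falls 0.25 to 0.5 SD more in the BFR arm, with no added variance: the observed difference is 0.75 to 0.50 SD and power is 54% to 28%.
- Swelling falls less in the BFR arm by the same amounts: the observed difference is 1.25 to 1.50 SD.
- No true muscle difference but a swelling difference of 0.25 to 0.5 SD: rejection rate 10.5% to 28% instead of 5%.

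**The case against.** The best defence is that each list, read alone, keeps the two outcomes on different instruments. A reader might infer that the plan uses the tape for both muscle and effusion. No single list says so, and the SAP already grades effusion from 0 to 3. The documented fault is a conflict between section 8 and the other two lists.

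A reader might also infer that girth cannot answer the objective at all, or that the arm difference is biased whatever happens. Neither follows. The objective is comparative, and swelling that resolves equally in both randomised arms drops out of the arm difference. Bias needs swelling at the tape site to differ by arm, and the documents do not show that it does. Nor do they support the idea that the band itself raises swelling; they describe its placement and tightness and say nothing of such an effect. The site matters too, since thigh girth well away from the joint would be less affected than girth at the knee.

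All of this stands. It leaves three things unanswered. The within-arm tests have no such cancellation. Equal swelling cannot be taken for granted when effusion is itself compared between arms. And the optional ANCOVA uses baseline values, so it does not address swelling that diverges after randomisation.

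**Conclusion.** The point holds in a limited form. The protocol contradicts itself on how hypertrophy and effusion are measured, and the SAP adopts the version in which muscle size is swelling-sensitive girth at an unstated site, starting from an immediate post-surgical baseline. The effect is most direct on within-arm change. On the between-arm difference it is a loss of precision if swelling is common to both arms, and a bias of either sign if it is not.

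The size rests on assumptions throughout: girth, muscle fraction, limb shape, muscle gain and the swelling difference are not in the documents. Under them a 5% muscle gain is worth about 0.5-0.9 cm of tape, and a swelling difference of 0 to 1 cm runs from no consequence to cancelling or mimicking that gain. This does not show that the trial's result will be wrong. It shows that a girth result alone is not a sufficient basis for a statement about hypertrophy.

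**What to change.** 1. Reconcile section 8, the Outcome Measures list and the SAP to one measure per outcome.
2. Keep effusion on the SAP's 0-3 clinical grade and delete circumference as the effusion measure in section 8.
3. If ultrasound/MRI was done, make it the hypertrophy endpoint in the SAP, with its own analysis.
4. If it was not, rename the tape endpoint *limb girth*, report the landmark actually used, and draw no conclusion on hypertrophy.
5. Optionally, tabulate girth alongside concurrent effusion grade by arm and timepoint. Label it descriptive, because effusion arises after randomisation and cells will be small at 16 per arm.

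The cost is wording in the outcome definitions and SAP, plus one optional table; bringing imaging into the SAP also adds its analysis. Section 7 lists enrolment as actual, so it may be too late to choose a tape site prospectively. That is why the fix asks for the site used and does not depend on new measurements. The downside is a more modest claim where imaging is absent.
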